#### **V. Vielight Neuro’s Mechanism of Action**

The therapeutic use of near-infrared energy, as delivered by the Vielight Neuro device, is often termed, low level light therapy (LLLT). It uses non-laser LEDs with a near infrared (NIR) wavelength of 810 nm. LLLT has been studied with regards to its effects on a variety of tissue types and clinical indications (Chung, Dai et al. 2012). Product codes have been established for a number of LLLT-based FDA-approved devices, including those for orthodontic treatment (PLH), lymphedema reduction (NZY), pain relief (NHN), hair growth (OAP), wrinkle reduction (OHS), herpes simplex virus cold sore healing (OKJ), fat reduction (OLI), acne treatment (OLP), and fungal infections of the nails (PDZ).

[figure not shown]
The putative mechanism of action underlying LLLT is termed photobiomodulation (PBM) which is the actions of photonic energy on cellular chromophores. Though the most well-known chromophore is chlorophyll in plants, mitochondrial cytochrome C oxidase (CCO) has also been demonstrated to absorb energy in the NIR range (Karu 1989; Karu and Kolyakov 2005). Also known as complex IV of the electron transport chain, CCO is a critical transmembrane protein with two copper centers and two heme groups, which are likely responsible for the NIR energy absorption. CCO is responsible for reducing cytochrome c and generating water while transporting 4 protons into the intermembrane space.

The involvement of CCO in the pathology of AD has been established through multiple studies (Salminen, Haapasalo et al. 2015; Onyango, Dennis et al. 2016). A post mortem brain examination of AD patients vs. healthy controls found a selective deficit of CCO activity in the temporal cortex and hippocampus of AD patients, but no differences in activity of the other mitochondrial respiratory chain enzyme complexes (Maurer, Zierz et al. 2000). Findings of decreased CCO activity in relevant regions of post mortem brains of AD patients has been observed by several different groups (Kish, Bergeron et al. 1992; Mutisya, Bowling et al. 1994; Parker, Parks et al. 1994; Bosetti, Brizzi et al. 2002). Neurons containing neurofibrillary tangles (Nagy, Esiri et al. 1999) or those composing senile plaques (Perez-Gracia, Torrejon-Escribano et al. 2008) from the post mortem brains of AD patients have both been demonstrated to have low CCO activity. Studies of animal models of AD also confirm that mitochondria in the vicinity of amyloid beta plaques (Xie, Guan et al. 2013), amyloid beta fragments (Canevari, Clark et al. 1999), or even amyloid beta precursor protein (Anandatheerthavarada, Biswas et al. 2003), demonstrate decreased CCO activity and evidence that this decrease occurs prior to the appearance of plaques (Manczak, Anekonda et al. 2006).

The absorption of NIR energy by CCO is believed to cause it to dissociate from nitric oxide (Karu, Pyatibrat et al. 2005; Lane 2006) which is an inhibitor of CCO and causes reduced overall ATP production and can even lead to cell death (Brown 2001). Both amyloid beta and amyloid beta precursor protein have been demonstrated in preclinical models to be capable of concurrently increasing nitric oxide levels, decreasing CCO activity and reducing ATP levels (Keil, Bonert et al. 2004; Keil, Bonert et al. 2004) while the reduction of brain amyloid beta levels by gelosin causes the opposite effects and inhibits apoptosis (Antequera, Vargas et al. 2009). Additionally, upregulation of nitric oxide synthase genes has been observed to correlate with disease severity in post mortem brains of AD patients (de la Monte and Wands 2006).

The resulting effects of LLLT are increased CCO activity (Wong-Riley, Liang et al. 2005), increased electron transport (Pastore, Greco et al. 1994), increased ATP production (Passarella, Casamassima et al. 1984; Karu, Pyatibrat et al. 1995), increased mitochondrial RNA and protein synthesis (Greco, Guida et al. 1989) as well as the modulation of reactive oxygen species leading to activation of nuclear factor kappa B (Chen, Arany et al. 2011), well established as crucially involved in hippocampal synaptic plasticity and memory (Albenisi and Mattson 2000; Meffert, Chang et al. 2003). With evidence growing for the hypothesis that mitochondrial dysfunction triggers amyloid beta accumulation (Swerdlow, Burns et al. 2014; Benek, Aitken et al. 2015), it is not surprising that transcranial LLLT has been demonstrated to reduce hyperphosphorylated tau, neurofibrillary tangles, amyloid beta plaques, fragments and precursor protein, while concurrently increasing mitochondrial function, restoring CCO activity and increasing ATP levels in several different transgenic mouse models of AD (De Taboada, Yu et al. 2011; Grillo, Duggett et al. 2013; Purushothuman, Johnstone et al. 2014; Purushothuman, Johnstone et al. 2015).

The Vielight Neuro delivers a synchronized pulse frequency of 40 Hz from all LED clusters. It had been observed that aberrant increases in network excitability and compensatory inhibitory mechanisms in the hippocampus may contribute to A $\beta$ -induced neurological deficits in mouse models (Palop et al. 2007). Electroencephalographic (EEG) recordings in mouse models indicated network hypersynchrony, primarily during reduced gamma oscillatory activity. Restoring gamma oscillatory may inhibit synaptic activity and gamma oscillations and reduced hypersynchrony, memory deficits, and premature mortality – conditions associated with AD (Verret et al. 2014). The gamma pulse frequency of 40 Hz has been demonstrated to attenuate amyloid beta proteins production in the hippocampus and modulate microglial activity resulting in increased scavenging of amyloid beta (Iaccarino, Singer et al. 2016) which may lead to improving AD conditions.

Finally, the Vielight Neuro has been designed to target the delivery of NIR energy to particular brain regions which are dysfunctional in AD patients, specifically the default mode network (DMN; see Figure 2A). The DMN is a set of brain regions that are concurrently active when an individual is left undisturbed to think to themselves (Shulman, Fiez et al. 1997; Mazoyer, Zago et al. 2001; Raichle, MacLeod et al. 2001). The DMN is also active when an individual is remembering the past, envisioning the future, and considering the thoughts and perspectives of others (Buckner and Carroll 2007). The core regions comprising the DMN (Figure 2B) include the medial prefrontal cortex (mPFC), the posterior cingulate/retrosplenial cortex (PCC/Rsp), the inferior parietal lobule (IPL), lateral temporal cortex (LTC), and hippocampal formation including the entorhinal cortex (Buckner, Andrews-Hanna et al. 2008). AD patients show a reduction in resting glucose metabolism and eventual atrophy in these DMN regions which progresses with disease severity (Minoshima, Giordani et al. 1997; Herholz, Salmon et al. 2002; Scahill, Schott et al. 2002; Thompson, Hayashi et al. 2003). Amyloid beta plaques have also been observed to selectively accumulate in DMN regions, even prior to the observation of symptoms (Klunk, Engler et al. 2004).

## VII. Study Overview:

Photobiomodulation (PBM) is a kind of light therapy that uses red or near-infrared light to stimulate, heal, regenerate, and protect tissue that has either been injured, is degenerating, or else is at risk of dying. Human cadaver studies have shown near-infrared wavelengths can penetrate 40-50 mm through the scalp and skull. Saltmarche et al. (2017) recently showed that 12-weeks of transcranial treatment with a commercially available PBM device (i.e., the Vielight "Neuro") benefits cognitive function in patients with mild-to-moderately severe dementia. Specifically, Saltmarche et al. (2017) reported improvements on the Mini Mental State Examination (MMSE,  $p<0.003$ ) and Alzheimer's Disease Assessment Scale-cognitive subscale (ADAS-cog,  $p<0.03$ ) in 5 dementia patients after 12-weeks of PBM treatment. Because it is important to show that these promising preliminary findings are not spurious findings, the first objective of this study is to replicate Saltmarche et al's findings that the effects of 12-weeks of PBM treatment can improve cognitive function in older adults with dementia. Because the Vielight Neuro device targets nodes of the default mode network (DMN), which is dysregulated in dementia (e.g., Alzheimer's disease (AD)), second aim of this pilot study is to investigate whether 12 weeks of PBM therapy with the Vielight Neuro device improves DMN connectivity in older adults with dementia. Because there is suggestive evidence that PBM therapy enhances blood flow, the third study aim will examine whether 12-weeks of PBM therapy improves cerebral blood flow (CBF) in older adults with dementia. The final study aim is to investigate the effects of PBM treatment on quality of life in older adults with dementia and on caregiver burden.

Ten pairs of older adults with dementia and their caregivers (CG) will be enrolled in a randomized, wait-list control trial. Five primary participants, PP, (i.e., individuals with dementia) will be randomized to start PBM treatment immediately with the Vielight Neuro device after the baseline psychometric and

MRI assessments. Five PP will be randomized to a "Delayed PMB" group that will not start treatment with the Vielight Neuro device until after the 12-week psychometric and MRI assessment. Cognitive function and quality of life will be assessed in all PPs at baseline, weeks 6, 12, 18, and 24. Caregiver burden, positive aspects of caregiving, depressive symptomology, and dementia-related behaviors in the PP will be assessed in all CGs at baseline, weeks 6, 12, 18, and 24. Neuroimaging measures will only be assessed in PPs at baseline and week 12.

**VII. Study Flow:**

**VIII. Study Aims:**

- 1) Replicate the findings of Saltmarche et al. (2017) that 12 weeks of PBM therapy improves cognitive function in patients with dementia.
- 2) Examine the effect of 12 weeks of PBM therapy on DMN functional connectivity in individuals with dementia.
- 3) Examine the effect of 12 weeks of PBM therapy on cerebral blood flow in individuals with dementia.
- 4) Examine the effects of 12 weeks of PBM therapy on quality of life in individuals with dementia and caregiver burden.
- 5) Determine if changes in cognition and quality of life are associated with changes in DMN functional connectivity and cerebral perfusion after 12 weeks of PBM therapy.

**IX. Study Hypotheses:**

- 1) Primary participants (PP) randomized to in the Immediate PBM group will show improved cognitive function after 12 weeks of near-infrared PBM therapy with the Vielight Neuro device compared to PP randomized to the Delayed PBM group.
- 2) Primary participants (PP) randomized to in the Immediate PBM group will show increased functional connectivity within nodes of the DMN after 12 weeks of near-infrared PBM therapy with the Vielight Neuro device compared to PP randomized to the Delayed PBM group.
- 3) PP randomized to Immediate PBM will show increased cerebral perfusion after 12 weeks of near-infrared PBM therapy with the Vielight Neuro device compared PP randomized to the Delayed PBM group.
- 4) Improvements in cognitive function (Alzheimer's Disease Assessment Scale-cognitive subscale, ADAS-cog, and the Montreal Cognitive Assessment, MOCA) and Quality of Life in Alzheimer's Disease (QOL-AD) scores will be correlated with increases in DMN functional connectivity and increases in cerebral perfusion after 12 weeks of PBM therapy with the Vielight Neuro in PP randomized to Immediate PBM.
- 5) Caregivers in the Immediate PBM group will experience greater reductions in caregiver burden (Caregiver Burden Inventory, CBI) and depressive symptomology and improvements in positive feelings about caregiving (Positive Aspects of Caregiving) after 12 weeks compared to caregivers in the Delayed PBM group.

**X. Study Population and Sample Size:**

We will study 10 dyads/pairs of individuals with dementia and their caregivers for this pilot, proof-of-concept study. Five individuals with dementia will be randomized to start PBM treatment with the Vielight Neuro device immediately after baseline assessments (Immediate PBM). Five individuals with dementia will be randomized to the Delayed PBM group, which will not start PBM treatment with the Vielight Neuro device until after completing Week 12 assessments. The sample size was chosen because this is what can be supported with the REAC and Department of Radiology Seed Grant funds. Also, because the Saltmarche et al. (2017) pilot study suggested that cognitive gains achieved by the dementia patients cannot be maintained once PBM treatments are discontinued, we plan to offer the Vielight Neuro devices to primary study participants upon completion of all study procedures so that

they may continue to use. Thus the sample size is also limited by the cost of the Vielight Neuro device (\$875 for research).

#### **XI. Recruitment and Screening:**

Two main methods will be used to recruit potential participants for the study. First, study co-investigator [name] will help identify and refer individuals with dementia and caregivers who have completed her Prevention of Loss of Independence through Exercise (PLIÉ) study, who meet study eligibility criteria, and who have consented to be contacted about future studies. Second, we will post flyers about the study at adult day programs in the San Francisco Bay Area and in public areas such as SF VAMC clinic waiting rooms and neighborhoods surrounding the study sites.

Legally Authorized Representatives (LARs) referred by [name] will be contacted by research staff, who will describe the study in more detail and will obtain verbal consent to screen the LAR and/or caregiver. Those who are interested and eligible will be scheduled for an in-person appointment to obtain written consent. For potential study participants not referred by [name] (e.g., they find out about the study through flyers posted in the community), initial eligibility will be determined by self-referral.

Potential eligibility for study participation will be determined by [name], [name], and the research team members. Potential eligibility will be determined in the protocol under the inclusion/exclusion criteria sections. LARs referred by [name] will be contacted by research staff who will describe the study in more detail and will obtain verbal consent to screen the LAR and/or caregiver. Those who are interested and eligible will be scheduled for an in-person appointment to obtain written consent. For potential study participants not referred by [name] (e.g., they find out about the study through flyers posted in the community), initial eligibility will be determined by self-referral.

The initial screening will be performed by telephone and will include assessment of demographics and eligibility criteria. Specifically, the LARs of potential study participants who have expressed interest in being contacted about the study will be screened for eligibility over the telephone. Basic demographic and medical history information also will be collected after obtaining verbal consent. This information will be collected during screening in order to compare characteristics of those who choose to participate or not to assess for potential selection biases. Those who are eligible and interested will then be scheduled for an in-person consent visit. LARs may also serve as the study caregiver (CG) or LARs may designate someone else (e.g., other family member, paid caregiver) to play this role. If an alternate study CG is designated, they will be screened and consented separately or consented with the LAR and potential participant if possible.

**XII. Consent Visit (in person, PP and LAR together):** Informed consent will be obtained with the primary study participant (PP) and LAR together at a location of their choosing (e.g., their home or the SF VAMC). Detailed consent procedures are provided in the Informed Consent section. Because the caregiver (CG) will also undergo psychometric assessment, s/he will be asked to sign a separate consent form. If an alternate CG is designated by the LAR, s/he may be consented with the primary participant or at another time and place. After consent has been obtained, global cognitive function, quality of life, and a MRI of the brain will be acquired in primary study participants.

A research staff member will ask the potential PP a series of yes/no questions to assess whether consent information was understood. The wording of the questions will be varied to ensure that primary study participants cannot simply answer yes or no to all questions. Information not understood will be

discussed again and understanding will be reassessed. If the PP is unable to answer questions after two discussions, s/he will be considered unable to provide consent and will be asked to assent to study procedures by agreeing to have their LAR provide consent on his/her behalf. PP who appear to dissent to study procedures (e.g., shake heads no, appear agitated or distressed) will be considered ineligible for the study even if their LAR provides consent.

Because the purpose of this study is to investigate whether PBM treatment delivered via the commercially available Vielight Neuro device can cognitive function in individuals with dementia, it is likely that some participants (i.e., individuals with dementia) will no longer have the capacity to consent for themselves due to the nature of their condition. A surrogate may be necessary to: a) provide consent should it be determined that the study participant does not have the capacity to make decisions; b) provide reliable information regarding the participant's current level of functioning including mental and physical functioning, relevant to the study and c) to provide information on caregiver burden resulting from the loss of independence of the participant.

Participants will never be forced to participate in the study or any of the study procedures. In addition, assessment of outcomes will be discontinued if there is evidence of distress or lack of assent.

We will use the following hierarchy if the PP, LAR, or CG differs regarding their desire to continue participation:

- 1) If the PP wishes to stop participating in the study (i.e., no longer consents/assents), the dyad of PP/CG will be withdrawn, regardless of the preferences of the CG or LAR.
- 2) If the PP does not demonstrate capacity to consent and the LAR wants the primary participant to stop participating in the study (i.e., withdraws consent on their behalf), the dyad will be withdrawn, regardless of the preferences of the PP or the CG.
- 3) If the CG wishes to stop participating in the study but the PP wishes to continue and, if the PP does not demonstrate capacity to consent, the LAR agrees (e.g., paid CG no longer wishes to be involved), then the PP will be allowed to continue without the CG's involvement.

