(Immediate [baseline-week 12] vs. Delayed [baseline-week 12]) to examine between-group differences for hypothesis 2. We will use Spearman's rank correlation analysis to examine the relationship between baseline-to-week 12 changes in DMN functional connectivity and CBF with baseline-to-week 12 changes in ADAS-cog, MOCA, and QOL-AD in the Immediate PBM group to test hypothesis 3. We will use a two sample t-test on the baseline vs. week-12 differences in CG measures (i.e., Caregiver Burden Inventory, Positive Aspects of Caregiving Scale, Geriatric Depression Scale) to examine between-group differences to test hypothesis 5. We will also evaluate the magnitude of treatment effects on the PP and CG psychometric measures using Cohen d effect sizes for the within-group difference in the Delayed PBM group (baseline-to-week 12 and week 12-to-week 24).

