### **XIV. Study Procedures:**

Baseline Psychometric Assessment (with PP and CG separately). The baseline assessment will take place after the consent visit and prior to randomization. PPs and CGs will be assessed separately so that their answers do not influence each other. PPs will be directly assessed by research staff while CGs will be

provided with self-administered forms when feasible or may complete the assessment in person, by phone or mail-in.

Baseline Assessments in PPs:

- Cognitive function (Montreal Cognitive Assessment MOCA). Cognitive function will be measured using the Montreal Cognitive Assessment, MOCA). The MOCA's score range is the same as the MMSE (0–30), but has additional, more complex tasks including executive function. Items address orientation, drawing figures, processing speed, naming objects, memory, recall, attention, vigilance, repetition, verbal fluency, and abstraction.
- Alzheimer's Disease Assessment Scale -- Cognitive Subscale (ADAS-cog). Cognitive function will also be assessed with the ADAS-cog, one of the most commonly used outcome measures in dementia drug treatment trials and one of the measures considered by the Food and Drug Administration (FDA) for approval of dementia medications. It includes direct assessment of learning (10-word list), naming (objects), following commands, constructional praxis (figure copying), ideational praxis (mailing a letter), orientation (person, time, place), recognition memory and remembering test instructions. The ADAS-cog is scored on an 80-point scale, with higher scores reflecting worse cognitive function.

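### Withdrawing a willing caregiver along with the person with dementia discards caregiver week-12 scores that hypothesis 5 needs: an avoidable loss, with possible bias of unknown size and direction

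*Combined protocol and SAP*

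**What the plan says.** Protocol section XII (Consent Visit) ends with a three-rule hierarchy for disagreement about continuing.

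- Rule 1: if the person with dementia (PP) no longer consents or assents, "the dyad of PP/CG will be withdrawn, regardless of the preferences of the CG or LAR".
- Rule 2: if the legally authorised representative (LAR) withdraws a PP who lacks capacity, "the dyad will be withdrawn, regardless of the preferences of the PP or the CG".
- Rule 3: if the caregiver (CG) stops but the PP wishes to go on, with the LAR's agreement where needed, "then the PP will be allowed to continue without the CG's involvement".

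The caregiver is a research subject in his or her own right: "Because the caregiver (CG) will also undergo psychometric assessment, s/he will be asked to sign a separate consent form". Section XIV has the pair assessed separately. Caregivers receive self-administered forms where feasible, or "may complete the assessment in person, by phone or mail-in".

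Hypothesis 5 (section IX) is about caregivers: "Caregivers in the Immediate PBM group will experience greater reductions in caregiver burden", together with depressive symptoms and positive feelings about caregiving. Its test appears in the Protocol Summary under Statistical Methodology: "We will use a two sample t-test on the baseline vs. week-12 differences in CG measures". The SAP does not mention hypothesis 5, missing data or an analysis set.

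**The concern.** The hierarchy separates the pair in one direction only. A PP may stay without the caregiver, but a caregiver may not stay without the PP, even when willing. Yet the Caregiver Burden Inventory (CBI), the Positive Aspects of Caregiving scale and the Geriatric Depression Scale (GDS) record the caregiver's own feelings and mood, and completing them does not need the PP.

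A caregiver withdrawn before week 12 has no change score and leaves the randomised comparison. With five caregivers per arm, one such loss is a large share of the data. If the reason for leaving is related to how the caregiver was faring, the remaining comparison is also biased. The point covers only the caregiver's own self-reports. Ending the PP's participation and assessments when the PP or LAR says so is not in question.

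**Working it through.** **Inputs from the documents.** Ten dyads, five per arm (section X). A two-sample t-test on change from baseline to week 12 (Protocol Summary). Alpha, sidedness, SD, power and withdrawal rate are not stated, and the sample size rests on funding and device cost, so there is no planned figure to reproduce.

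**Assumptions.** Two-sided alpha 0.05; normal change scores with equal SD, results in SD units; one caregiver measure at a time.

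**1. Share of data.** One caregiver of five is 1/5 = 20% of an arm. Withdrawal after week 12 does not affect the hypothesis 5 test.

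**2. Chance of at least one lost dyad.** With independent withdrawal at rate q before week 12, this is 1 − (1 − q)^10:

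| Assumed q | At least one of 10 lost |
|---|---|
| 5% | 40% |
| 10% | 65% |
| 20% | 89% |
| 30% | 97% |

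**3. Precision.** The half-width is t(0.975, df) × √(1/n₁ + 1/n₂).

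- 5 v 5: t(8) × √0.40 = 2.306 × 0.632 = 1.46 SD
- 4 v 5: t(7) × √0.45 = 2.365 × 0.671 = 1.59 SD

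The standardised difference detectable with 80% power (exact noncentral t) rises from 2.02 to 2.19.

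**4. Possible bias from one lost caregiver, no true effect.** The expected extreme of five standard normal values is 1.163 SD from the mean. Removing the worst moves the mean of the other four by 1.163/4 = 0.29 SD in the favourable direction for that arm. If the reason for leaving correlates ρ with the caregiver's change, the expected shift is ρ × 0.29:

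| Link between leaving and the caregiver's change | Expected shift |
|---|---|
| None (ρ = 0) | 0 |
| ρ = 0.5 | about 0.145 SD |
| Complete (lost caregiver has the worst change of five) | 0.29 SD |

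In the last case, a simulation of 400,000 null trials puts significant results favouring the depleted arm at 6.4%, against the nominal 2.5%. The relevant caregiver is the one with the worst change, who need not be the one with the highest burden.

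**5. Direction.** Selective loss of badly faring caregivers from the Immediate arm would flatter PBM. The same loss from the Delayed arm would work against it.

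**The case against.** A reader might infer that the lost caregivers are those for whom things went badly, so that the rule tilts hypothesis 5 towards PBM. The documents do not support that. They give no withdrawal rates or reasons. Section XII says that "assessment of outcomes will be discontinued if there is evidence of distress or lack of assent", but that describes the PP's distress, not the caregiver's burden. Section XX lists claustrophobia, scanner noise and distress at testing as risks, and both arms have the same scans and assessments up to week 12. Immediate PPs also have home sessions in that period, hence more occasions to refuse, but whether this leads to selective loss is conjecture.

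Other objections stand in part.

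- **0.29 SD and 6.4% are the extreme case.** Even that shift is less than half the 5 v 5 standard error (0.29 against 0.63 SD), and the comparison is very imprecise with or without the loss.
- **Rule 2 reaches less far than it seems.** Section XI allows the LAR to be the study caregiver. Rule 2 then overrides no separate caregiver wish; it matters only where someone else fills that role.
- **Recovery will be partial.** Burdened caregivers may be the least willing to go on, and those who quit themselves fall under rule 3.
- **The consent text is not visible.** The caregiver form, and any terms it has on later contact, could not be checked.
- **The hierarchy protects the PP.** This is a good reason to withdraw the PP fully and to stop reports about the PP. It does not require discarding the caregiver's separately consented answers about his or her own state.

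This is also a narrow part of a wider gap, since the SAP omits hypothesis 5 and has no missing-data rule.

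**Conclusion.** The point holds as an avoidable loss of data with possible bias. Rules 1 and 2 withdraw a willing caregiver, and no visible text restores that caregiver's week-12 scores. Each dyad lost before week 12 costs 20% of an arm; one loss takes the half-width from 1.46 to 1.59 SD, on the assumed two-sided 0.05. The expected bias from one loss runs from zero to 0.29 SD, according to a link between leaving and the caregiver's change that the documents do not describe, and its sign depends on the arm. Bias in favour of PBM is a possibility, not a finding.

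Severity is optional: this is a conditional loss for one of five hypotheses in a ten-dyad pilot. The remedy is cheap enough to be worth making.

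**What to change.** Reword rules 1 and 2 in section XII along these lines: *the PP is withdrawn; a caregiver who agrees under his or her own consent will be asked to complete the CBI, Positive Aspects of Caregiving and GDS at the remaining scheduled weeks, at least week 12, by mail or phone.* Analyse these caregivers in their randomised arm for hypothesis 5. After PP withdrawal, collect no caregiver reports about the PP (Neuropsychiatric Inventory, proxy QOL-AD) unless the PP or LAR agrees.

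The cost is a sentence in the protocol, matching wording in the caregiver consent form, an IRB amendment and a few mailed forms or calls. There are two downsides: some caregivers will decline, so not all of the loss is recoverable, and scores given after the PP has left reflect assignment to PBM rather than continued use.
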